Appendix D. Severity Assessment Criteria Score

Severity assessment criteria score (JDA total score) specified by the Japanese Dermatological Association

A	Assessment of skin symptoms: erythema, pustules, Edema (0 – 9)		
B	Systemic symptoms/assessment of test findings: fever, WBC count, serum CRP, serum albumin (0 – 8)		
o Severity:	Mild	Moderate	Severe
(Total score)	(0 – 6)	(7 – 10)	(11 – 17)

A Assessment of skin symptoms (0 – 9)

	Severe	Moderate	Mild	None
Erythema area (total)*	3	2	1	0
Erythema area with pustules **	3	2	1	0
Edema area **	3	2	1	0

* % vs. BSA (severe: $\geq 75\%$, moderate: $\geq 25\%$ and $< 75\%$, mild: $< 25\%$)

** % vs. BSA (severe: $\geq 50\%$, moderate: $\geq 10\%$ and $< 50\%$, mild: $< 10\%$)

B Systemic symptoms/assessment of test findings (0 – 8)

Score	2	1	0
Fever ($^{\circ}\text{C}$)	≥ 38.5	≥ 37 and < 38.5	< 37
WBC count ($/\mu\text{L}$)	$\geq 15,000$	$\geq 10,000$ and $< 15,000$	$< 10,000$
Serum CRP (mg/dL)	≥ 7.0	≥ 0.3 and < 7.0	< 0.3
Serum albumin (g/dL)	< 3.0	≥ 3.0 and < 3.8	≥ 3.8

Overall Improvement Rating Defined According to JDA Total Score

JDA Total Score Change		Other Criteria	
Markedly improved	Decreased by \geq 3 points	or	No or little symptom of generalized pustular psoriasis
Moderately improved	Decreased by 1 or 2 points	or	\geq 30% reduction of erythema area with pustules compared to baseline, without reaching "no or little symptoms of generalized psoriasis" or, Clinically meaningful improvement in at least 2 of the other parameters of the severity assessment criteria (erythema area, oedema area, WBC count, CRP, fever, serum albumin) AND the sum of the changes in individual JDA components is < 3
Slightly improved	0 points (no change)	and	\geq 20% and $<$ 30% reduction of erythema area with pustules compared to baseline, or, Clinically meaningful improvement in at least 1 of the other parameters of the severity assessment criteria (erythema area, oedema area, WBC count, CRP, fever, serum albumin)
Unchanged	0 points (no change)	and	Does not fulfil the other criteria of "slight improvement"
Worsened	Increased by \geq 1 point	-	-

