6.0 Analysis Conventions

Since this is an open-label continuation study, no statistical test will be conducted. Summary statistics will be provided. Data from preceding studies will be integrated with data from this study in the summaries.

Definition of Baseline

For this study, baseline values are defined as the last non-missing values prior to the first dose of study drug in this study. These baseline values will be referred to as "BL" in this document. Unless otherwise specified, this will be the "baseline" for analysis.

Definition of Rx Days (Days Relative to the Date of First Dose of Study Drug)

Rx days are calculated for each time point relative to the date of first dose of this study. They are defined as the number of days between the day of the first dose of risankizumab and the specific time point. Rx days are negative values when the time point of interest is prior to the first risankizumab dose day. Rx days are positive values when the time point of interest is on or after the first risankizumab dose day. The day of the first dose of risankizumab is defined as Rx Day 1, while the day prior to the first risankizumab dose is defined as Rx Day –1 (there is no Rx Day 0).

Definition of Analysis Windows

All time points and corresponding time windows are defined based on Rx Days.

For efficacy analyses, local tolerability, laboratory parameters, and vital sign variables, analysis windows are constructed using the following algorithm:

- Determine the nominal Rx day for each visit (e.g., Week 4 [4 weeks after Baseline visit] equals Rx Day 28).
- In order to include all post baseline data, the first post-baseline interval starts on the first day and the time after the first dose of risankizumab (Rx Day 1).
- Determine the window around a specific nominal Rx day, are presented in the Protocol Appendix C.
- If more than one assessment is included in a time window the assessment closest to the nominal day will be used. If there are two observations equidistant to the nominal day, the one after the nominal day will be used in analyses. If more than one post baseline assessment is included on the same

day, then the worst assessment on that day will be used in analyses, except those specified in Section [11.0](#).

The protocol specified visits and corresponding time windows used in the efficacy analyses, local tolerability, laboratory parameters, and vital sign variables, are presented in the following [Table 1](#) – [Table 32](#).

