10.2 Primary Efficacy Endpoints

The following key efficacy variables will be summarized at all visits in the ITT population for each disease:

For GPP:

- Proportion of subjects achieving a GPP Clinical Response according to JDA total score, defined as at least "Slightly Improved" in the overall improvement rating from baseline, at Week 16.

For EP:

- Proportion of subjects achieving an EP Clinical Response, defined as at least "Minimally Improved" in Clinical Global Impression-Global Improvement (CGI-GI) at Week 16.

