10.3 Secondary Efficacy Endpoints

The following additional efficacy variables will be summarized at all visits in the ITT population:

For GPP:

- Proportion of subjects achieving a GPP Clinical Response at Week 52
- Proportion of subjects achieving $\geq 90\%$ reduction from baseline Psoriasis Area Severity Index (PASI) score (PASI 90) at Week 16
- Proportion of subjects achieving PASI 90 at Week 52

For EP

- Proportion of subjects achieving an EP Clinical Response at Week 52
- Proportion of subjects achieving PASI 90 at Week 16
- Proportion of subjects achieving PASI 90 at Week 52

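### Protocol Appendix D can place one GPP assessment in both a responder and a non-responder row, and neither document says which row prevails

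*Protocol*

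**What the plan says.** Protocol 5.3.3 defines GPP Clinical Response through the overall improvement rating in Appendix D. *Markedly*, *Moderately* and *Slightly improved* are responses; *Unchanged* and *Worsened* are not.

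The relevant rows of Appendix D are:

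- *Moderately improved*: "Decreased by 1 or 2 points or \geq 30% reduction of erythema area with pustules compared to baseline". The pustule-area route is limited to subjects short of near-clearance ("compared to baseline, without reaching 'no or little symptoms of generalized psoriasis"). A second route needs clinically meaningful improvement in at least two other parameters. The cell ends "AND the sum of the changes in individual JDA components is < 3", without saying whether this covers one route or both, or how the changes are signed.
- *Slightly improved*: a 0-point change together with a pustule-area reduction of at least 20% but below 30%, or improvement in at least one other parameter.
- *Unchanged*: a 0-point change and "Does not fulfil the other criteria of 'slight improvement".
- *Worsened*: "Worsened Increased by \geq 1 point". Its other-criteria cell holds only a dash.

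SAP 10.2 restates the primary endpoint ("Proportion of subjects achieving a GPP Clinical Response according to JDA total score") and SAP 10.3 the secondary one ("Proportion of subjects achieving a GPP Clinical Response at Week 52"). Neither adds a derivation. Protocol 8.1 leaves complete analysis details to the SAP, and the SAP's own appendix is marked not applicable.

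**The concern.** The rows are not mutually exclusive, and the overlap crosses the line between response and non-response. One assessment can satisfy two stated rules that give opposite values of the primary endpoint.

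The rating is the primary efficacy result for Substudy GPP at Week 16 and a secondary one at Week 52. No hypothesis is tested, so the proportion and its 95% confidence interval (SAP 10.1) are the reported result. Appendix C schedules a responder rating at visits, SAP Table 1 windows it like other assessments, and Protocol 5.5.5.1 says allocation is not concealed. An unguided choice between rows would therefore be made with the dose known. The same response status is used for uptitration in the Protocol synopsis, Protocol 3.2 and 5.5.4, and SAP 4.2.

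**Working it through.** **Scoring table.** Three skin components scored 0–3 and four systemic components scored 0–2 give 3×3 + 4×2 = 17, which matches the stated range of 0–17.

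**An eligible example.** Protocol 5.2.1 requires pustule area of at least 10% BSA and a JDA total below 14. The values below are illustrative and are scored with the Appendix D cut-offs. In every follow-up column the pustule area falls from 40% to 25%: (40 − 25)/40 = 37.5%.

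| Component | Baseline | 0-point case | +1 case | +2 case |
|---|---|---|---|---|
| Erythema 60% | 2 | 2 | 2 | 2 |
| Pustule area 40%, then 25% | 2 | 2 | 2 | 2 |
| Edema 5% | 1 | 1 | 1 | 1 |
| Temperature 36.8 (37.2 in +1 and +2) | 0 | 0 | 1 | 1 |
| WBC 9,500 (10,200 in +2) | 0 | 0 | 0 | 1 |
| CRP 1.0 | 1 | 1 | 1 | 1 |
| Albumin 3.5 | 1 | 1 | 1 | 1 |
| **Total** | **7** | **7** | **8** | **9** |

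- The +1 and +2 cases meet *Moderately improved* through the pustule-area route and *Worsened* through the score.
- The 0-point case meets *Moderately improved*. It also meets *Unchanged*: 37.5% lies outside the 20% to <30% band of *Slightly improved*, and no other parameter improved.

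**Why the pustule score need not move.** The middle band runs from 10% to <50%. A fall of exactly 30% leaves the score unchanged for baseline areas from 10/0.7 = 14.3% to <50%, and from 50/0.7 = 71.4% upward. For a 37.5% fall the limits are 10/0.625 = 16% and 50/0.625 = 80%.

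**Does the '< 3' clause remove the overlap?** Eight readings were tested: two scopes (last route only, or both routes) by four sums.

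- Last route only (four readings): the pustule-area route is not restricted.
- Both routes: the net rise is 1 or 2, the net fall is −1 or −2, the absolute net change is 1 or 2, and the sum of absolute component changes is 1 or 2. All are below 3.

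So the +1 and +2 cases meet both rows in 8 of 8 readings.

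For other profiles with a net rise of 1 or 2, the overlap always holds if the clause is a net or signed sum, or covers the last route only. If it is a sum of absolute changes over both routes, some profiles drop out. For example, a pustule score falling by 1 while two others rise by 1 gives a net of −1 + 1 + 1 = +1 but an absolute sum of 3. An enumeration of score profiles (baseline pustule score 2 or 3, total below 14) kept 7,733 of 507,417 at +1 and 17,549 of 406,327 at +2 under that reading. These are counts of combinations, not probabilities.

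For a rise of 3 or more, the overlap depends on the reading, so the point is limited to rises of 1 or 2.

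**Near-clearance.** A subject who reaches it leaves the pustule-area route but meets *Markedly improved* through that row's own 'or', so a score rise still conflicts with *Worsened*.

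**Effect of one subject.** Protocol 8.2 gives at least 8 GPP subjects and Protocol 5.5.3 a 1:1 ratio, so 4 per arm at the minimum. The shift is 1/n: 1/4 = 25 points in an arm, 1/8 = 12.5 pooled. If more enrol (an assumption), it is 1/5 = 20 or 1/6 = 16.7 points per arm. With exact Clopper-Pearson intervals (assumed, as the SAP names no method):

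- arm: 3/4 = 75% (19.4–99.4) against 4/4 = 100% (39.8–100)
- pooled: 7/8 = 87.5% (47.3–99.7) against 8/8 = 100% (63.1–100)

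**The case against.** The best defence is the structure of the table. Rows run from best to worst, and the exclusions point only upward: *Moderately* excludes near-clearance, *Slightly* stops below 30%, and *Unchanged* excludes the slight-improvement criteria. Read top-down, each case gets one answer, and it is response. This is plausible, but neither document says it and no wording ties it to *Worsened*. The phrase 'according to JDA total score' in the endpoint could suggest the opposite, because in the conflicting cases that score has risen.

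Second, if the site records one rating per visit, the dataset holds one value. That stands, but it only moves the choice to a rater who knows the dose and has no written rule.

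Third, SAP 6.0 has a tie rule: "then the worst assessment on that day will be used in analyses". It chooses between several assessments on one day, not between two rows met by one assessment.

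Fourth, the printed layout of the *Moderately improved* cell may show what the '< 3' clause covers. It may, but the worked cases conflict under either scope.

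Fifth, the effect is limited, and this stands. The conflict needs a net score rise, or no change, despite a fall in pustule area. No test is planned, and SAP 10.4 also reports JDA total and component changes, PASI and PGA-GPP.

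**Conclusion.** The concern holds in conditional form. A GPP assessment with a pustule-area reduction of at least 30% and a net rise of 1 or 2 points can meet both *Moderately improved* and *Worsened*. A 0-point change with such a reduction and no other improvement literally meets both *Moderately improved* and *Unchanged*. This is a contradiction between written rules of the primary endpoint and should be fixed.

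A reader might infer more than the documents support:

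- That every such subject meets both rows. Under an absolute-sum reading of the '< 3' clause over both routes, many score profiles with a net rise of 1 or 2 do not.
- That the GPP result is biased. The documents give neither frequency nor direction, and known allocation makes bias possible, not shown.
- That the defect is worth 25 points. That figure is 1/n for any reclassified subject in an arm of 4, and the example intervals overlap heavily.
- That the 0-point case should plainly count as response. The table does not settle it, and because response status also governs uptitration, this review does not settle it either.

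**What to change.** Before the Week 28 interim, at which SAP 4.4 has the Week 16 endpoints analysed, the sponsor should reconcile the *Moderately improved*, *Unchanged* and *Worsened* rows, and state the scope and sign of the '< 3' clause, so that each assessment falls in exactly one row. This belongs in SAP 10.2 and 10.3 now, and in Appendix D at the next amendment.

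If it is not settled in time, report the GPP response proportion twice: once with conflicting assessments counted as responses and once as non-responses.

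Check recorded ratings by program for the numeric routes only (total-score change and percent reduction in pustule area), and list the conflicts. Near-clearance and clinically meaningful improvement are judgements with no numeric definition, so a program cannot reproduce the whole rating.

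Which row prevails is for the sponsor. The Protocol synopsis, Protocol 3.2 and 5.5.4, and SAP 4.2 use the same response status and must refer to the reconciled definition. No clinical rule is proposed here.

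The cost is a little SAP text, one check and possibly one extra table. Editing Appendix D is a protocol amendment that needs IEC/IRB approval (Protocol 9.1).

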Appendix E. Psoriasis Area and Severity Index (PASI)

The PASI score is an established measure of clinical efficacy for psoriasis medications (Study R96-3541).

The PASI is a tool which provides a numeric scoring for subjects overall psoriasis disease state, ranging from 0 to 72. It is a linear combination of percent of surface area of skin that is affected and the severity of erythema, infiltration, and desquamation over four body regions.

The endpoints used are based on the percent reduction from baseline, generally summarized as a dichotomous outcome based on achieving over an X% reduction (or PASI X), where X is 50, 75, 90 and 100.

To calculate the PASI score, the four main body areas are assessed: **head (h), trunk (t), upper extremities (u) and lower extremities (l)**. These correspond to 10, 30, 20 and 40% of the total body area respectively.

The area affected by psoriasis within a these four areas site is estimated as a percentage of the total area of that anatomic site and assigned a numerical value according to the degree of psoriatic involvement as follows:

- 0 = no involvement
- 1 = < 10%
- 2 = 10% to < 30%
- 3 = 30% to < 50%
- 4 = 50% to < 70%
- 5 = 70% to < 90%
- 6 = 90% to 100%

The **signs of severity, erythema (E), infiltration (I) and desquamation (D)** of lesions are assessed using a numeric scale 0 – 4 where 0 is a complete lack of cutaneous involvement and 4 is the severest possible involvement; scores are made independently

for each of the areas, h, t, u and l and represents a composite score for each area. The signs of severity, **erythema (E)**, **induration (I)** and **desquamation (D)** of lesions are assessed using a numeric scale 0 – 4:

- 0 = No symptoms
- 1 = Slight
- 2 = Moderate
- 3 = Marked
- 4 = Very marked

The table below outlines the characteristics of each category.

	Erythema^a	Desquamation	Induration
0 = none	No redness	No scaling	No elevation over normal skin
1 = slight	Faint redness	Fine scale partially covering lesions	Slight but definite elevation, typically edges indistinct or sloped
2 = moderate	Red coloration	Fine to coarse scale covering most of all of the lesions	Moderate elevation with rough or sloped edges
3 = marked	Very or bright red coloration	Coarse, non-tenacious scale predominates covering most or all of the lesions	Marked elevation typically with hard or sharp edges
4 = very marked	Extreme red coloration; dusky to deep red coloration	Coarse, thick, tenacious scale over most or all lesions; rough surface	Very marked elevation typically with hard sharp edges

a. Do not include residual hyperpigmentation or hypopigmentation as erythema.

Assignments for the following body regions are as follows:

- Neck: include with the head
- Buttocks: include with the lower extremities
- Axillae: include with the trunk
- Genitals: include with the trunk

- The inguinal canal separates the trunk and legs anteriorly

The PASI score for each body region is obtained by multiplying the sum of the severity scores by the area score, then multiplying the result by the constant weighted value assigned to that body region. Since the head, upper extremities, trunk, and lower extremities correspond to approximately 10%, 20%, 30%, and 40% of BSA, respectively, the PASI score is calculated using the formula.

The PASI score is calculated according to the following formula:

$$\text{PASI} = 0.1(\text{Eh}+\text{Ih}+\text{Dh})\text{Ah} + 0.3(\text{Et}+\text{It}+\text{Dt})\text{At} + 0.2(\text{Eu}+\text{Iu}+\text{Du})\text{Au} + 0.4(\text{El}+\text{Il}+\text{Dl})\text{Al}$$

where E, I, D, and A denote erythema, induration, desquamation, and area, respectively, and *h*, *u*, *t*, and *l* denote head, upper extremities, trunk, and lower extremities, respectively. PASI scores range from 0.0 to 72.0 with the highest score representing complete erythroderma of the severest degree.

Appendix F. Diagnosis and Assessments for Subjects with Psoriatic Arthritis

At Visit 1, subjects with a positive history of PsA or suspected to have PsA will be further evaluated for PsA diagnosis based on CASPAr (ClASsification of Psoriatic Arthritis) criteria (Study R15-1001). To be classified as having PsA, a subject must have inflammatory articular disease (joint, spine, or enthesal) with at least 3 points total from the 5 categories below. All trial participants will have 2 points assigned due to evidence of current psoriasis per trial entry criteria and require at least one additional point for diagnosis of PsA.

CASPAr Criteria

Category	Point Assignment
Evidence of current psoriasis, a personal history of psoriasis, or a family history of psoriasis	2 points
Typical psoriatic nail dystrophy, including onycholysis, pitting, or hyperkaratosis observed on current physical examination	1 point
A negative test result for rheumatoid factor by any method except latex	1 point
Either current dactylitis, defined as swelling of an entire digit, or a history of dactylitis recorded by a rheumatologist	1 point
Radiographic evidence of juxta-articular new bone formation appearing as ill-defined ossification near joint margins (but excluding osteophyte formation) on plain radiographs of the hand or foot	1 point

Appendix G. Clinical Global Impression-Global Improvement (CGI-GI)

Clinical Global Impression (CGI)

2. Global improvement: Rate total improvement whether or not, in your judgement, it is due entirely to drug treatment.

Compared to his condition at admission to the project, how much has he changed?

Reproduced from Guy W, editor. ECDEU Assessment Manual for Psychopharmacology. 1976. Rockville, MD, U.S. Department of Health, Education, and Welfare

Appendix H. Patient Reported Outcomes

Dermatology Life Quality Index

The DLQI is a subject-administered, ten-question, quality of life questionnaire that covers six domains including symptoms and feelings, daily activities, leisure, work and school, personal relationships and treatment (Study R05-2548). The DLQI has a 1-week recall period. Item scores range from 0 (not relevant) and 1 (not at all) to 3 (very much).

Question 7 is a "yes"/"no" question where "yes" is scored as 3.

The DLQI will be self-administered by the subject at visits indicated in the [Appendix C](#).

[figure not shown]
The DLQI will be analyzed under six headings as follows:

Domain	Question Number	Score
Symptoms and feelings	Questions 1 and 2	Score maximum 6
Daily activities	Questions 3 and 4	Score maximum 6
Leisure	Questions 5 and 6	Score maximum 6
Work and school	Question 7	Score maximum 3
Personal relationships	Questions 8 and 9	Score maximum 6
Treatment	Question 10	Score maximum 3

DLQI total score is calculated by summing the scores of each question resulting in a range of 0 to 30 where 0 – 1 = no effect on subject's life, 2 – 5 = small effect, 6 – 10 = moderate effect, 11 – 20 = very large effect, and 21 – 30 = extremely large effect on subject's life. The higher the score, the more the quality of life is impaired. A 5-point change from baseline is considered a clinically important difference.

If the answer to one question in a domain is missing, that domain is treated as missing. If 2 or more questions are left unanswered (missing), DLQI total score is treated as missing.

The DLQI has been extensively used in clinical trials and has a large evidence base supporting reliability and validity (Study R15-3845).

Appendix I. PGA Scale for Generalized Pustular Psoriasis

The Physician's Global Assessment of Generalized Pustular Psoriasis is a 6-point scale used to measure the severity of skin disease at the time of the qualified investigator's evaluation of the subject. The degree of overall severity will be evaluated using the following categories: erythema, pustulation, and edema.

Scoring Instructions:

If a subject has signs of erythema, pustulation, or edema intermediate between two grades, then the subject's erythema, pustulation, or edema grade should be assigned the higher of the two grades. For example, if a subject's erythema is considered to be worse than 'mild' but less than 'moderate,' the subject's erythema grade should be considered 'moderate.'

The subject's score is an arithmetic average (mean) of the grades for erythema, pustulation, and edema, rounded to the nearest whole integer. For example, if a subject's erythema is moderate (3), **pustulation** is mild (2), and edema is moderate (3), the average grade is 2.67, which is rounded to the nearest whole integer of 3, giving the subject a score of 'moderate.'

Grade	Erythema	Pustulation	Edema	Score
0	No evidence of erythema	No evidence of pustulation	No evidence of edema	Cleared, except for residual discoloration
1	Faint erythema	Scattered isolated pustules	Minimal edema	Minimal
2	Light red coloration	A cluster of non-confluent pustules involving 1 skin location	Mild edema	Mild
3	Moderate red coloration	Clusters of non-confluent pustules involving more than 1 skin location	Moderate edema	Moderate
4	Bright-red coloration	A confluent 'lake of pus' in 1 skin location	Marked edema	Severe
5	Dusky to deep-red coloration	Confluent 'lakes of pus' in more than 1 skin location	Severe edema	Very severe

